## 1 Introduction

GoFresh is an individual level, randomized feeding trial to determine the effect of 12 weeks of dietitian-assisted DASH-patterned grocery shopping on seated blood pressure in 150-176 adults in the ages of 18-100 years. Participants are randomly assigned to one of 2 groups: (1) Dietitian-assisted, DASH-patterned grocery shopping or (2) Self-directed grocery shopping group. The trial is organized into two phases: the intervention phase (assessed at 3 months) and the observation (maintenance) phase with physical assessments at 6-months and behavioral assessments at 6 and 12 months. The primary trial analysis described in this document focuses on physical assessments at 3 and 6 months. Other outcome assessments performed during the study (i.e., qualitative interviews as well as questions related to quality of life, grocery shopping and dining habits, and perceived stress) are not planned as part of this analysis.

The **primary outcome** is the net effect of DASH groceries with reduced sodium, DASHpatterned groceries versus self-directed grocery shopping on 12-week seated systolic blood pressure (as measured at 3 months, the end of the intervention phase).

#### 1.1 Primary aim

To determine the effects of 12-weeks of dietitian-assisted, home-delivered, virtuallyordered, low sodium, DASH groceries compared with self-directed grocery shopping (DASH education and a \$500/month stipend over 3 months) on seated office systolic blood pressure among Black adults.

In this randomized controlled trial (RCT) of at least 150 participants, we will compare the DASH grocery intervention versus the self-directed group over 12 weeks to determine its effect on seated systolic blood pressure.

#### 1.2 Other aims

To estimate the effects of the DASH grocery intervention on the following secondary outcomes:

- Measured at 6 months (observation phase):
  - Seated, office-based, systolic blood pressure (SBP)
- Measured at 3-month and 6-month visits (intervention & observation phase):
  - Seated, office-based, diastolic blood pressure
  - Ambulatory blood pressure monitoring (ABPM): wake-time systolic and diastolic blood pressure
  - Body Mass Index (BMI)
  - 24-hour urine sodium
  - 24-hour urine potassium
  - Hemoglobin A1c

- Lipids: total cholesterol, high density lipoprotein cholesterol, derived low density lipoprotein cholesterol, and triglycerides
- Serum potassium
  Serum creatinine
- Daily intake of fat, fruits, and vegetables
- 24-hour dietary recall

## 2 Data Source

Data pertaining to the recruitment drive of the GoFresh Trial will be managed in a secure Excel document that will be accessible to team members for tracking recruitment activities. These data include the total number of inquiries (both enrolled and non-enrolled persons).

Data for all screened and randomized participants will be entered by clinic staff into a REDCap dataset (Vanderbilt University, Nashville, Tennessee). REDCap is a secure, password-protected, web-based, research data capture and management application, hosted by the REDCap eData Collection Core of Beth Israel Deaconess Medical Center.

Grocery nutrient information will be derived from the ESHA Research platform (Beaverton, Oregon) and Nutrition Data System for Research (NDSR, University of Minnesota, Minneapolis, Minnesota). Backup files of the database will be generated and stored at regular intervals in a secure, independent location, to permit regeneration of the database in the event that it is destroyed. Data from ambulatory blood pressure monitoring (ABPM) (Sentinel, Spacelabs Healthcare, Snoqualmie, Washington), laboratory results (Quest Diagnostics, Secaucus New Jersey), and the Automated Self-Administered 24-hour Dietary Assessment Tool (ASA24, U.S. Department of Health and Human Services, Washington D.C.) will be regularly uploaded into REDCap to create a centralized analytic dataset.

## 3 Primary Outcome: Seated Blood Pressure

#### 3.1 Randomization and primary analysis

Participants will be randomized using a permuted block scheme (sizes of 2, 4, or 6) through a randomization feature embedded in REDCap in strata of baseline BP (SBP 120 to <140 mm Hg or 140 to <150 mm Hg). Blood pressure will be used as a stratification variable to ensure that people with varying degrees of hypertension are evenly distributed between interventions.

Randomization assignments will follow a 1:1 ratio such that half of participants will be assigned to order home-delivered, low-sodium, DASH-patterned groceries with the assistance of a registered dietitian over a 12-week period. The other half will be assigned to self-directed grocery shopping. This group will receive a handout about the DASH diet and receive a \$500 monthly stipend for 3 months.

#### 3.2 Primary analysis

Our primary comparison is the net effect of randomized assignment (dietitian-assisted vs. self-directed shopping) on office SBP from baseline to 3- (primary) and 6-months post-randomization. Office SBP will be based on the average of three visits at baseline (two screening visits and the randomization visit each with 3 measurements; nine measurements total), two 3-month follow-up visits (each with 3 measurements; six measurements total), and two 6-month follow-up visits (each with 3 measurements; six measurements total). We will first confirm that the residuals of office SBP are normally distributed (if not it will be log-transformed). Modeling will be performed using generalized estimating equation (GEE) models with a treatment-by-visit interaction term. We will perform an intent-to-treat analysis. The visit term will be used to compare changes between 3 months versus baseline, 6 months versus 3 months, and 6 months versus baseline with a product (interaction) term to compare changes across intervention. Models will be adjusted for ZIP code or baseline blood pressure in sensitivity analyses.

Our hypothesis is that 12 weeks of dietitian-assisted, home-delivered, low sodium, DASH groceries will lower office SBP compared to 12-weeks of self-directed grocery shopping. The null hypothesis is that there will be no difference in office SBP between the two intervention arms. The comparison between the two treatment groups will be performed by comparing the regression coefficient for treatment with zero (a two-sided alpha of <0.05 will be considered statistically significant for the primary comparison at 3-months.

For additional pre-specified sensitivity analyses and subgroups to assess effect medication, see below.

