#### 3.3 Power and sample size

The primary outcome is change in SBP between the two randomized assignments. Our power calculation is based on the 12-week means and variances from the DASH-Sodium trial, where the 12-week between-group difference in SBP was -8.9 mm Hg. With 75 people in each arm, we will have sufficient power to detect a difference in SBP of -5.8 mm Hg (type 1 error of 0.05, power of 0.85; assuming a standard deviation of 11.85 and 11.4 for control and intervention groups based on the DASH-Sodium trial). We will over-recruit up to at least 176 participants to account for a 15% attrition rate.

With respect to secondary endpoints, we will have sufficient power to detect small differences of 15% or less in the following secondary endpoints: wake-time SBP, BMI, cholesterol, triglycerides, and hemoglobin A1c. Regarding adherence, we will be able to detect changes of 13.0%–29.5% in self-reported fruit and vegetable intake, urine sodium and potassium, and 24-hour recall potassium. These differences are smaller in magnitude than the actual differences observed in prior trials.

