## 5 Missing data

We will employ a number of recommended strategies to prevent missing data:

- A simplified data collection schedule that minimizes participant burden;
- Intention-to-treat analysis that includes following participants according to the data collection schedule regardless of compliance with the study intervention;
- Frequent engagement with the participants through visit reminder calls or notes;
- Contiguous windows of time during which specific follow-up visits are allowed;
- Monetary incentives to encourage enrollment and continued participation;
- Rigorous training of clinic staff emphasizing the importance of
  - Positive and warm interpersonal relationships between the participants and study staff
  - Study commitment during the consent process to ensure that potential participants understand the importance of completing the study
  - $\circ$   $\,$  Addressing participant concerns to minimize dissatisfaction  $\,$
  - $\circ$   $\,$  Collecting data even if a participant discontinues the study treatment
  - Reasons for any drop-outs will be documented.

We will perform the following sensitivity analyses using established methods for addressing missingness in clinical trials: use of out-of-window blood pressure measurements, multiple imputations at the individual level, and best and worst-case scenarios. We will compare the results from these approaches with primary analysis results to assess the primary result's robustness to the effects of missing data. Further, we will compare the baseline characteristics of complete cases and participants with missing measures between the two assignments.

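### The primary GEE leaves its working correlation and missing-data assumption unstated and omits baseline SBP as a covariate, so under working independence arm-differential dropout could bias the 3-month contrast

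*SAP*

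**What the plan says.** SAP 3.2 defines the primary comparison as the effect of assignment "on office SBP from baseline to 3- (primary) and 6-months post-randomization" and gives the model in one sentence: "Modeling will be performed using generalized estimating equation (GEE) models with a treatment-by-visit interaction term". The test is two-sided: "a two-sided alpha of <0.05 will be considered statistically significant for the primary comparison at 3-months". Protocol section 13 adds a Gaussian distribution with identity link.

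Neither document names a working correlation for any outcome. A robust variance estimator is stated only for the secondary endpoints (SAP 4.2). Adjustment for baseline blood pressure (or ZIP code) is a sensitivity analysis in SAP 3.2, although SAP 3.1 stratifies randomisation on baseline SBP.

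On attrition, SAP 3.3 says: "We will over-recruit up to at least 176 participants to account for a 15% attrition rate". The primary analysis takes measurements inside the 3-month window (SAP 3.4, Sensitivity analyses), with no imputation or weighting mentioned. SAP section 5 lists, as sensitivity analyses, out-of-window readings and "multiple imputations at the individual level, and best and worst-case scenarios". It also plans to compare baseline characteristics of complete cases and participants with missing measures by assignment.

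**The concern.** A GEE with an arm-by-visit mean can give different 3-month contrasts on the same incomplete data, depending on the working correlation. Under independence, the change in each arm is the mean of those seen at 3 months minus the baseline mean of everyone randomised. People who leave stay in the second mean but not in the first. If those who leave had unusually high or low baseline SBP, and this pattern differs by arm, the contrast shifts.

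An arm difference is plausible. Assignment is known to participants. The DASH arm has weekly calls and is asked to eat only the study groceries, whereas the self-directed arm receives a stipend and one scheduled call (Protocol section 11). What is at stake is the headline estimate: two analysts could both follow SAP 3.2 and report different primary results.

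**Working it through.** **1. The plan's own figure.** SAP 3.3 gives "With 75 people in each arm, we will have sufficient power to detect a difference in SBP of -5.8 mm Hg" under "type 1 error of 0.05, power of 0.85; assuming a standard deviation of 11.85 and 11.4 for control and intervention groups".

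- Root-mean-square SD = √((11.85² + 11.4²)/2) = 11.63.
- n per arm = 2 × 11.63² × (1.960 + 1.036)² / 5.8² = 72.2, so 73 (stated 75).
- Power at 75 per arm is 0.863 (normal) or 0.859 (t), against 0.85.
- SE of a difference in means = 11.63 × √(2/75) = 1.90; detectable difference = 2.996 × 1.90 = 5.69.
- 150/0.85 = 176.5, against 176.

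The sample size reproduces and is not in question.

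**2. Bias under working independence.** Let β be the slope of 3-month SBP on baseline SBP: β = correlation × 11.63 / baseline SD. Let s be the mean baseline SBP of completers minus that of everyone randomised, in a given arm. Then

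bias = β × (s in DASH − s in self-directed).

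If s is the same in both arms, the bias is zero.

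**3. Inputs the documents do not give (assumptions).** Dropout is 15% in each arm and logistic in baseline SBP. The log-odds slope is 0.08 per mm Hg in one arm and −0.08, 0, 0.04 or 0.08 in the other. The correlation is 0.5 or 0.7. The baseline SD is 11.63 (equal to follow-up) or 7.5 (entry is restricted to 120 to <150 mm Hg).

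A slope of 0.08 gives s = −0.645 mm Hg at SD 7.5 and −1.457 at SD 11.63. A slope of 0.04 gives −0.334 and −0.789.

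Worked case, SD 7.5 and correlation 0.5: β = 0.5 × 11.63/7.5 = 0.775.
- One arm only: 0.775 × (−0.645) = −0.50.
- Opposite slopes: 0.775 × (−0.645 − 0.645) = −1.00.
- Unequal, same direction: 0.775 × (−0.645 + 0.334) = −0.24.

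Bias in mm Hg:

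| Baseline SD | Correlation | Opposite (0.08, −0.08) | One arm (0.08, 0) | Unequal (0.08, 0.04) | Same in both |
|---|---|---|---|---|---|
| 7.5 | 0.5 | −1.00 | −0.50 | −0.24 | 0 |
| 7.5 | 0.7 | −1.40 | −0.70 | −0.34 | 0 |
| 11.63 | 0.5 | −1.46 | −0.73 | −0.33 | 0 |
| 11.63 | 0.7 | −2.04 | −1.02 | −0.47 | 0 |

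The negative sign (favouring DASH) follows from giving DASH the positive slope. Reversing the slopes reverses the sign. A separate large simulation, with dropout odds ratios of 2 to 3 per baseline SD, gave −0.57 to −1.17 for one arm and −1.13 to −2.29 for opposite dependence.

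**4. Does naming another correlation suffice?** In that simulation, exchangeable or unstructured GEE with a common scale left 0 to −0.14 when baseline and follow-up variances were equal. With a baseline SD of 7.5 it left −0.21 to −1.14. A common-scale model corrects with a slope near the working correlation, which is too small when baseline SBP varies less than follow-up SBP.

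**5. Baseline adjustment.** Regressing 3-month SBP on arm and baseline SBP gave bias within 0.05 in every scenario. With 75 per arm and complete data:

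- Adjusted SE = 11.63 × √(1 − r²) × √(2/75) = 1.64 at r = 0.5 and 1.36 at r = 0.7.
- Change-score SE = √(11.63² + SD₀² − 2r × 11.63 × SD₀) × √(2/75) = 1.67 to 1.90 at r = 0.5 and 1.36 to 1.47 at r = 0.7, for SD₀ from 7.5 to 11.63.

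Adjustment does not cost precision.

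**The case against.** A reader might infer that the primary analysis relies on data missing completely at random. The documents do not say so. That assumption is tied to working independence, which they never choose. A Gaussian, identity-link GEE with a well-specified correlation and variance is close to a likelihood analysis. What the plan assumes is undetermined.

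A reader might also infer that any baseline-related dropout biases the contrast. It does not: dependence that is the same in both arms cancels.

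Three further points have weight. First, opposite slopes are an adverse case, with higher-SBP people leaving one arm and lower-SBP people leaving the other; nothing in the documents predicts this. Second, leaving the groceries is not the same as missing the outcome. Protocol section 11 has staff encourage those who stop groceries to attend for blood pressure, and uses the week-8 call in the self-directed arm to schedule the 3-month visit. SAP section 5 commits to follow-up regardless of compliance. Third, the planned baseline adjustment, multiple imputation and comparison of completers with non-completers address this mechanism and could expose it.

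All three limit the likely size. They do not close the gap, because the documents give no rule for what is concluded if a sensitivity analysis disagrees with the primary result.

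**Conclusion.** The point holds as a conditional one. The primary model is under-specified, and it omits as a covariate the variable that would protect it. The bias arises only if working independence is used and dropout depends on baseline SBP differently by arm. Under the assumptions above it is then about 0.2 to 0.5 mm Hg for unequal slopes in the same direction and 0.5 to 1.0 for dependence in one arm only. Opposite slopes give 1.0 to 2.0, which is 1.00/1.67 = 0.6 to 2.04/1.47 = 1.4 standard errors, or 17% to 35% of the 5.8 mm Hg target. It is zero for equal dependence. The slopes, correlations and baseline SDs are assumed, so these figures show scale and are not a forecast. Sample size and power are unaffected. The change is worth making because the better model is already in the plan as a sensitivity analysis and costs nothing in precision.

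**What to change.** In SAP 3.2, with matching wording in Protocol section 13:

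- Make the baseline-SBP-adjusted model primary. Either use baseline SBP as a covariate for the 3- and 6-month values, or fit a repeated-measures model with baseline means constrained equal across arms and an unstructured covariance.
- In the covariate form, take baseline out of the outcome vector. If it stays as a response and is also a covariate with one common slope, that slope is pulled towards 1 and the bias is not reliably removed.
- Specify robust standard errors for the primary model, and state that missingness is assumed to depend only on observed data.
- Keep the unadjusted GEE, with its working correlation named, as a sensitivity analysis beside the missing-data analyses in SAP section 5.

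Naming a working correlation alone would not be enough if baseline variance is below follow-up variance. The cost is SAP and protocol wording; N, visits and data are unchanged. The one downside is a modelling assumption for the relation between baseline and follow-up SBP. The change does not address dropout that depends on unobserved follow-up SBP, so the best- and worst-case analyses should stay.

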10. RANDOMIZATION AND MASKING

After screening, consenting participants will be 1:1 randomized to the DASH grocery or self-directed arm using web-based, password-protected, randomization software following a permuted block scheme (sizes of 2, 4, or 6). Participants and staff directly administering the intervention will be informed of randomization assignments, but they will be masked to study results until after the study is complete. Meanwhile, staff who perform clinic assessments and the study investigators will be masked to randomization assignments.

The randomization schemes will be generated by the Beth Israel Deaconess Medical Center biostatistician using permuted block methods. Randomly-varying block sizes of 2, 4 and 6 will be used. Randomization will be stratified by baseline systolic blood pressure: 120-139 mm Hg or 140-<150 mm Hg (stage II hypertension) in order to ensure balanced treatment assignments in each BP group.⁵⁹ Details of the block sizes will be concealed from study staff and investigators and generated prior to the study and added to the data management system/REDCap for digital randomization. Randomization tables will be uploaded to REDCap corresponding to the two BP strata. A designated staff member that is unblinded (most commonly our dietitian interventionist) will randomize participants by clicking on a digital randomization button in REDCap after informed consent, confirmation of eligibility, reviewing details of the intervention, and signing an intervention understanding form. This will be performed in a private location in the clinical research center away from other study staff. Once the assignment is revealed in REDCap, this information will be shared with the study dietitian, who will provide instructions pertinent for each intervention phase. Intervention assignment will not be shared with research coordinator or assistants performing data assessments or with study investigators. Other members of the study team will not be able to access this assignment information in REDCap. Study personnel and investigators will not be unmasked until follow-up and all data collection are completed.

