#### 3.4 Secondary Pre-specified Subpopulations Analysis

We will repeat the primary analysis to evaluate the effect of the intervention within the following subpopulations:

- 1. Age (≥65 vs < 65 years)
- 2. Biologic sex (female or male) based on index participant
- 3. Meal preparer status of the index participant
- 4. Baseline body mass index (≥30 vs <30 kg/m^2)
- 5. Baseline hemoglobin A1c (5.7 to <6.5%, <5.7%)
- 6. Family size (single family versus more than 1 participant)
- 7. Baseline SBP (following the randomization scheme)

We will fit generalized estimating equations restricted to the strata of interest. Threeway interaction product terms will be used to assess effect modification by baseline characteristic. Note these analyses are contingent on having sufficient number of participants in each strata. The strata involving baseline SBP will be performed regardless of number, following our randomization scheme.

Other stratified or subpopulations analyses based on baseline characteristics may be performed for hypothesis generation beyond the main study.

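### The primary SBP model is an unadjusted difference in change: baseline SBP and the randomisation stratum are left out, and the form of the planned sensitivity adjustment is not stated

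*SAP*

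**What the plan says.** SAP 3.2 builds the outcome from averaged readings: "Office SBP will be based on the average of three visits at baseline", followed by two visits at 3 months and two at 6 months. It then specifies a GEE with a treatment-by-visit interaction. The visit contrasts include 3 months against baseline, "with a product (interaction) term to compare changes across intervention". Baseline is therefore part of the response. SAP 3.3 agrees: "The primary outcome is change in SBP between the two randomized assignments".

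The same section describes the test as "comparing the regression coefficient for treatment with zero". On covariates it says only: "Models will be adjusted for ZIP code or baseline blood pressure in sensitivity analyses". Protocol 13 repeats that sentence.

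Randomisation is stratified on baseline SBP in two levels, below 140 and 140 to <150 mm Hg (Protocol 10, SAP 3.1). SAP 3.1 gives the purpose: "Blood pressure will be used as a stratification variable to ensure that people with varying degrees of hypertension are evenly distributed between interventions". The stratum is not in the primary model. Its one explicit analytic use is as a subgroup in SAP 3.4: "The strata involving baseline SBP will be performed regardless of number, following our randomization scheme".

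The working correlation is not stated. A robust variance is named only for the secondary endpoints (SAP 4.2).

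**The concern.** Three things follow from this specification.

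- **Precision.** A raw difference in change uses baseline only as a subtraction. In large samples, regressing follow-up SBP on baseline is never less precise.
- **Stratification.** Stratified randomisation balances baseline SBP between arms. A model without the stratum or baseline SBP gives its standard error no credit for that balance.
- **The sensitivity analysis.** If baseline BP or ZIP code is added as a main effect while baseline stays a response visit, the 3-month interaction cannot move with complete data. Agreement would then be built in, and a reader could mistake it for robustness to baseline adjustment. If the term is baseline by visit, or a covariate on follow-up SBP, it is a genuine adjustment. The plan does not say which.

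There is also loose wording about the tested term. With baseline as the reference visit, the treatment main effect is the baseline difference between arms. The term that compares changes is the interaction.

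**Working it through.** **Inputs from the documents.** 75 per arm, difference -5.8 mm Hg, SDs 11.85 and 11.4, power 0.85, 15% attrition, at least 176 recruited (SAP 3.3); two-sided 0.05 (SAP 3.2); entry SBP 120 to <150 mm Hg (Protocol 5).

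**Assumed, because not in the documents.** The correlation rho between baseline and 3-month SBP, and the baseline SD s0. I use s0 from 6.5 to 8.66; the upper value is a uniform spread over the entry range, 30/√12 = 8.66.

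**Step 1: the plan's own figure.** Pooled SD s1 = √((11.85² + 11.4²)/2) = 11.63. Noncentral-t power at 5.8 with 75 per arm is 0.859, which reproduces the stated 0.85.

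**Step 2: the two variances, reading 11.63 as the 12-week SD.**
- Change: SD_change² = s0² + s1² - 2·rho·s0·s1
- Baseline-adjusted: SD_adj² = s1²(1 - rho²)
- Difference: (s0 - rho·s1)², which is never negative. It is zero only when the slope of follow-up on baseline, rho·s1/s0, equals 1.

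Example, rho 0.3 and s0 8.66: SD_change = 12.24 and SD_adj = 11.09. The adjusted model matches the planned precision with 75 × 11.09²/12.24² ≈ 62 per arm.

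| rho | planned power (s0 8.66 to 6.5) | adjusted power | n per arm for the planned precision |
|---|---|---|---|
| 0.3 | 0.822-0.867 | 0.889 | 62-70 |
| 0.4 | 0.873-0.904 | 0.912 | 66-73 |
| 0.5 | 0.921-0.938 | 0.939 | 70-75 |
| 0.6 | 0.962-0.966 | 0.967 | 73-75 |

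Planned power falls below 0.85 only if rho is under 0.26 (s0 6.5) or 0.36 (s0 8.66). At -8.9 mm Hg it is at least 0.986 even at rho 0.2.

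**Step 3: reading 11.63 as the SD of change.** Solve s0² + sF² - 2·rho·s0·sF = 11.63² for the follow-up SD sF, then SD_adj = sF√(1 - rho²). The planned contrast keeps 0.859. The adjusted model has 0.881-0.929 (rho 0.3), 0.864-0.896 (rho 0.4) or 0.859-0.869 (rho 0.5).

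**Step 4: does a main effect change anything?** In one simulated data set of 176 people with complete data, the planned 3-month interaction was -4.84507 (SE 1.573796). Adding baseline BP or the stratum as a main effect gave the same values to six decimals, under independence and exchangeable working correlation. The follow-up model with baseline by visit and stratum gave -4.840807 (SE 1.432495). The algebra is the same for any covariate constant over visits, including ZIP code.

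With 15% dropout completely at random (2,000 trials per setting), the main-effect version moved single-trial estimates by a mean absolute 0.23-0.36 mm Hg (independence) or 0.12-0.13 (exchangeable), with no shift on average. Robust SEs under independence, without small-sample correction:

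| rho, s0 | planned | main effect added | follow-up model |
|---|---|---|---|
| 0.3, 8.66 | 1.97 | 1.96 | 1.80 |
| 0.3, 6.5 | 1.87 | 1.86 | 1.80 |
| 0.5, 8.66 | 1.73 | 1.69 | 1.63 |
| 0.5, 6.5 | 1.68 | 1.64 | 1.63 |

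**Step 5: whole-trial simulation.** 176 randomised, stratified permuted blocks, 15% dropout, small-sample-corrected robust SE, 6,000 trials per setting (Monte Carlo error about 0.005 for power, 0.003 for type I error).

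| rho, s0 | planned power | adjusted power |
|---|---|---|
| 0.3, 8.66 | 0.838 | 0.888 |
| 0.3, 6.5 | 0.859 | 0.878 |
| 0.5, 8.66 | 0.916 | 0.931 |
| 0.5, 6.5 | 0.922 | 0.931 |

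At rho 0.3 and s0 8.66 the planned SE averages 1.99 against a true sampling SD of 1.89, with type I error 0.038. At rho 0.3 and s0 6.5 it is calibrated (0.052). Over all settings type I error was 0.038-0.052 planned and 0.047-0.056 adjusted. Without the correction it was 0.044-0.059 and 0.055-0.060.

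**The case against.** The planned contrast is valid and answers the question SAP 3.2 and 3.3 pose, which is about change. The larger gains come from a low assumed correlation. At rho 0.3 the slope of 3-month on baseline SBP is only 0.40 (s0 8.66) or 0.54 (s0 6.5), yet baseline averages nine readings over three visits, which argues for a steeper slope. At an assumed slope of 0.8-0.9 the gain is 0 to 0.6 power points. The miscalibrated SE appears in one corner of the simulations and errs on the conservative side. This stands: the gain may be small, and nobody can say from the documents where in the range the trial will fall.

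The change is also not wholly free. Participants with no follow-up SBP leave the adjusted model, and SAP 5 plans multiple imputation only as a sensitivity analysis. The robust SE needs a stated small-sample correction, and Protocol 13 needs the same edit as the SAP. These points stand but are minor, because people without follow-up add almost nothing to the 3-month contrast.

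Finally, reading the sensitivity covariate as a main effect is an inference. The plan could mean a follow-up model, and its baseline blood pressure could even be the two-level stratum. The three-way subgroup models in SAP 3.4 would also involve the stratum. None of this puts baseline SBP or the stratum in the primary model, and the ambiguity is itself the reason to write the form down.

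**Conclusion.** The concern holds as a point of precision and specification. The primary estimate is not biased and the sample size is not wrong. Three parts rest on no assumed value: baseline SBP and the stratum are absent from the primary model, the form of the sensitivity adjustment is unstated, and a main-effect adjustment changes nothing with complete data.

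The size of the gain does rest on assumed rho and baseline SD. At -5.8 mm Hg on the 12-week reading, it runs from about 2 to 7 power points at rho 0.3 to under 2 points at rho 0.5. It is negligible for power if the true effect is near -8.9. The change should be made because the covariates are already recorded for everyone randomised and, in large samples, adjustment is never less precise.

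**What to change.** In SAP 3.2 and Protocol 13:

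1. Make the primary model a GEE on 3- and 6-month SBP with treatment, visit (3 months as reference), treatment by visit, continuous baseline SBP by visit, and the randomisation stratum.
2. Name the treatment coefficient at 3 months as the tested term.
3. State the working correlation, and state a robust SE with a small-sample correction.
4. Keep the unadjusted treatment-by-visit GEE as a sensitivity analysis.
5. Enter ZIP code in the baseline-adjusted follow-up model or with a visit interaction, and write down which.

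The cost is wording in both documents and a few lines of code. No new data are needed. Participants with no follow-up SBP leave the primary model, so SAP 5 should say that the planned multiple imputation is applied to this model as the check on their omission.

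### SAP 3.2 ties the primary significance test to the treatment coefficient, but the change contrast that the section defines is carried by the treatment-by-visit product term

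*SAP*

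**What the plan says.** SAP 3.2 describes the primary comparison as the "net effect of randomized assignment (dietitian-assisted vs. self-directed shopping) on office SBP from baseline to 3- (primary") and 6 months. The model is a GEE with a treatment-by-visit interaction. The visit term covers all pairwise comparisons among baseline, 3 months and 6 months, so baseline is a level of visit and baseline SBP is a response. The between-arm part of those comparisons is made "with a product (interaction) term to compare changes across intervention". Protocol section 13 (Effectiveness & Adoption) and SAP 4.2 use the same structure, and SAP 3.3 states: "The primary outcome is change in SBP between the two randomized assignments".

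The second paragraph of SAP 3.2 gives the null: "The null hypothesis is that there will be no difference in office SBP between the two intervention arms". It then sets the decision rule: "The comparison between the two treatment groups will be performed by comparing the regression coefficient for treatment with zero", at a two-sided 0.05 that "will be considered statistically significant for the primary comparison at 3-months". Neither document states a reference visit, and neither says that the coefficient for treatment means the product term.

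**The concern.** A model with treatment, visit and their product has no single coefficient that can be called the treatment effect. The coefficient labelled treatment is the arm difference at whichever visit is the reference, and the product terms hold the differences in change. The SAP gives the comparison of changes to the product term in one paragraph and puts the significance threshold on the other coefficient in the next.

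This is the only sentence in either document that ties the significance threshold to a model parameter. SAP 3.3 and protocol section 13 also give a type 1 error of 0.05 for SBP, but as an input to the sample size. A programmer who follows the sentence literally would report a number whose meaning depends on the software's reference level. To obtain the contrast that the section defines, the programmer has to override the sentence. That choice concerns the trial's one primary test and should be settled in writing before unmasking.

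**Working it through.** **1. The plan's own power figure.** Inputs from SAP 3.3: 75 per arm, difference 5.8 mm Hg, SDs 11.85 and 11.4, type 1 error 0.05, power 0.85.

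- Pooled SD = sqrt((11.85^2 + 11.4^2)/2) = sqrt((140.42 + 129.96)/2) = 11.627
- SE = 11.627 x sqrt(2/75) = 1.899
- Noncentrality = 5.8/SE = 3.055 (unrounded SE), on 148 df
- Two-sided power = 0.859 by noncentral t, or 0.863 by normal approximation

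The stated 0.85 reproduces.

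**2. What each coefficient is.** Let D0, D3 and D6 be the arm differences (DASH groceries minus self-directed) at baseline, 3 months and 6 months. Let A be the treatment indicator and V3, V6 the visit indicators. With baseline as reference:

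mean SBP = b0 + b1 A + b2 V3 + b3 V6 + b4 (A x V3) + b5 (A x V6)

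The arm difference is b1 at baseline and b1 + b4 at 3 months. So b1 = D0 and b4 = D3 - D0. The other codings follow in the same way. The values below put in D0 = 0 (randomised arms) and D3 = -5.8 (SAP 3.3). D6 is not given in the documents, so a range is assumed.

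| Reference visit | Coefficient for treatment | Expected value | Where the 3-month change contrast (D3 - D0 = -5.8) sits |
|---|---|---|---|
| Baseline | D0 | 0 | treatment x 3-month: -5.8 |
| 3 months | D3 | -5.8, a level difference | treatment x baseline: +5.8, sign reversed |
| 6 months | D6 | 0, -2.9 or -5.8 (assumed) | treatment x 3-month minus treatment x baseline |

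Fitting the GEE to a small complete data set with these arm means gave the same coefficients under independence and exchangeable working correlation. They are exact mean contrasts and need no assumed SD or correlation.

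**3. Level against change.** D3 and D3 - D0 have the same expected value under randomisation. In one realised trial with complete data, their estimates differ by exactly the observed baseline difference between arms, and their standard errors generally differ too. They are different tests with the same target under randomisation.

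**4. Illustration of the literal reading.** Simulated GEE fits (exchangeable, robust SE) used 75 per arm, complete data, the SAP's SDs at every visit, D0 = 0 and D3 = -5.8. The assumptions, which are not in the documents, were D6 = -2.9 and a between-visit correlation r of 0.5 or 0.7.

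- Baseline reference, treatment coefficient: mean 0.08 (r = 0.5) and -0.08 (r = 0.7); rejected in 6.9% and 6.4% of 1,000 runs, near the nominal 5%.
- Same fits, treatment x 3-month: mean -5.84 and -5.88; rejected in 87.0% and 97.0%.
- 3-month reference, r = 0.5, treatment coefficient: mean -5.83; rejected in 86.2% of 600 runs.

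The documents give no within-person correlation, so these rejection rates show the mechanism only. They are not a power claim for the trial.

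**The case against.** The strongest defence is that the sentence is shorthand. It comes directly after the interaction model, and it ends by saying that the threshold "will be considered statistically significant for the primary comparison at 3-months". A baseline arm difference cannot be a comparison at 3 months, so the sentence itself excludes the most damaging reading. This stands. A reader might infer that the trial will test a baseline difference, or that its primary test has almost no power; the documents do not support either inference.

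A second defence is that the documents are mixed on level versus change. SAP 1 describes the primary outcome as the "net effect of DASH groceries with reduced sodium, DASHpatterned groceries versus self-directed grocery shopping on 12-week seated systolic blood pressure", which can be read as a level at 3 months. SAP 1.1 and the protocol's definition of the primary outcome speak of SBP rather than change, and the null names neither a visit nor a change. With 3 months as reference, the treatment coefficient is a valid test of that null. This also stands, and SAP 1 should not be cited as support for change. It does not rescue the sentence. The opening of SAP 3.2, its product-term sentence and SAP 3.3 describe change, and the reference to 3 months does not choose between the two contrasts.

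A third defence is that the algebra shows only what reference coding always does and quantifies no harm to this trial. That is fair, and it limits the weight of the point.

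**Conclusion.** The concern holds as a wrongly named test parameter. With baseline as the reference visit, the coefficient named in the decision sentence has expected value 0 when the 3-month effect is -5.8 mm Hg. With 3 months as reference, it is the 3-month level difference, a legitimate comparison but not the change contrast that SAP 3.2 and 3.3 describe. With 6 months as reference, it is the arm difference at the visit whose SBP SAP 1.2 lists among the secondary outcomes ("Measured at 6 months (observation phase"). Under none of these codings is it the difference between arms in change from baseline to 3 months.

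The conclusion rests on reference-level coding of visit and on baseline being a level of visit, as SAP 3.2 says. It does not rest on any assumed correlation. It is not evidence that the wrong test will be run. The sample size and the stated power stand. The sentence should be corrected because, followed literally, it fails, and because it governs the single primary test.

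**What to change.** In SAP 3.2, state that baseline is the reference visit and replace the decision sentence with: *The primary hypothesis is tested by the treatment x 3-month interaction coefficient (difference between arms in change in office SBP from baseline to 3 months), two-sided alpha 0.05.* Reword the null to match: *no difference between arms in change in office SBP from baseline to 3 months.* The 6-month SBP comparison is already secondary in SAP 1.2 and needs no further change.

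The cost is two or three sentences of SAP text, best made before unmasking. Data collection, sample size and trial conduct are unaffected.
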